4.2.4. Supplementary Analyses

Table 5 summarizes the supplementary analyses that will be produced for the primary endpoint.

The purpose of these supplementary analyses is to provide additional insights for the primary efficacy results in selected groups of the study population.

Table 5: Supplementary Analyses

Supplemental Analysis	Applied Cohorts	Population	Handling of IEs	
Randomized Set analysis	LN and IgAN cohorts	Randomized Set	 Analysis and handling of IEs will be the same as in the primary analysis Only performed if the FAS excludes more than 10% of the Randomized Set 	
mFAS analysis	LN and IgAN cohorts	mFAS	 Analysis and handling of IEs will be the same as in the primary analysis Only performed if the mFAS excludes more than 10% of the FAS 	
PPS analysis	LN and IgAN cohorts	PPS	Analysis and handling of IEs will be the same as in the primary analysis	
Treatment policy analysis	LN and IgAN cohorts	FAS	The primary endpoint will be analyzed in the same manner as in the primary analysis except that all observed data will be used, regardless of receipt of additional standard of care therapy (LN cohort only) or treatment discontinuation	

Abbreviations: FAS = Full Analysis Set; IE = intercurrent event(s); IgAN = Immunoglobulin A Neuropathy; mFAS = Modified Full Analysis Set; PPS = Per-Protocol Set

In addition, the same ANCOVA model as described in Section 4.2.2 will be used for the primary efficacy analysis to compare reductions in proteinuria between the ALXN2050 Total and placebo groups.

4.3. Secondary Endpoint Analysis

The secondary efficacy analyses will be based on the FAS. These analyses will be descriptive in nature and no adjustment for multiplicity will be performed.

The analyses for participants in the LN cohort and participants in the IgAN cohort will be conducted and reported separately. Participants in each disease-specific cohort will be analyzed as randomized, regardless of actual treatment received.

The estimands for the key secondary analyses are defined in Table 6.

Table 6: Estimands for Key Secondary Analyses

Estimand	Population	Variable	Intercurrent Event	Population-level Summary
Key secondary analysis (continuous)	FAS	 Percentage change in proteinuria from baseline to Week 50 (both cohorts) Change from baseline in eGFR at Weeks 26 and 50 (both cohorts) 	 Receipt of additional standard-of-care therapy for a protocol-defined renal flare or suboptimal response (LN cohort only) Treatment discontinuation 	 Mean difference of percentage change in proteinuria from baseline in each treatment group Mean change in eGFR from baseline in each treatment group
Key secondary analysis (binary)	FAS	 Achieving > 30% and > 50% reduction in proteinuria at Weeks 26 and 50 compared to baseline (both cohorts) Meeting the criteria for CRR at Weeks 26 and 50 (LN cohort only) Meeting the criteria for PRR at Weeks 26 and 50 (LN cohort only) Meeting the criteria for partial remission at Weeks 26 and 50 (IgAN cohort only) 	Receipt of additional standard-of-care therapy for a protocol-defined renal flare or suboptimal response (LN cohort only) Treatment discontinuation	Response rate in each treatment group

Abbreviations: CRR = complete renal response; eGFR = estimated glomerular filtration rate; FAS = Full Analysis Set; LN = lupus nephritis; PRR = partial renal response

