- Endpoint: Percentage change from baseline to Week 26 in proteinuria
- Treatment: ALXN2050 180 mg bid versus placebo
- Intercurrent events: Receipt of additional standard of care therapy (LN cohort only) or treatment discontinuation
- Population-level summary: Difference in mean percentage change in proteinuria between ALXN2050 180 mg bid and placebo groups

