4.1.4. Handling of Dropouts or Missing Data

No imputation will be performed for missing baseline values. For missing postbaseline data not due to IEs, no imputation will be performed.

To derive duration of disease, partial date of diagnosis will be imputed as follows:

- If day is missing, it will be imputed to the "01"
- If day and month are missing, they will be imputed to "January 01"

Partial concomitant medication start dates and AE start dates will follow the same imputation rule to derive study phase.

Missing outcome data due to the COVID-19 pandemic (eg, dropout due to COVID-19) is assumed missing-at-random (MAR).

Missing outcome data due to dosing pause is assumed MAR.

Missing data for quality-of-life (QoL) instruments will be handled as specified in the instructions for each instrument in Section 6.3.

The following may occur during the study:

- Receipt of additional standard-of-care therapy (LN cohort only)
- Treatment discontinuation (LN and IgAN cohorts)
- Dosing pause

The handling of IEs is detailed in each analysis section.

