4.3.1. Secondary Endpoints

4.3.1.1. Percentage Change in Proteinuria from Baseline to Week 50 (Both Cohorts)

The percentage change from baseline in proteinuria at Week 50 will be analyzed using a mixed-effect model for repeated-measures (MMRM) using all available data up to Week 50 (either complete or partial). The data after the intercurrent events will be treated as missing. The model will include change from baseline in log-transformed proteinuria as the response variable and fixed, categorical effects of treatment sequence group, randomization stratification factor, visit, and treatment sequence group by visit interaction as well as a fixed, continuous effect of baseline log proteinuria as a covariate. An unstructured covariance matrix will be used to model the correlations among repeated measurements within each participant. If this analysis fails to

converge, a first-order autoregressive covariance matrix will be used. The Kenward-Roger approximation will be used to estimate denominator degrees of freedom.

For the LN cohort, the treatment effect will be evaluated for the ALXN2050 180 mg bid and placebo treatment groups using a contrast for treatment group-by-visit term at Week 50. The point estimate and 2-sided 90% CI for the mean difference of log-transformed proteinuria will be back-transformed (via exponentiation) to obtain the GMR and corresponding 2-sided 90% CI. The values will then be expressed as percentage change in adjusted geometric mean of proteinuria at Week 50 relative to baseline. The treatment effect will be evaluated for the ALXN2050 120 mg & 180 mg bid and placebo treatment group in the same model mentioned above.

For the IgAN cohort, participants initially randomized to the placebo treatment group will switch to receive either ALXN2050 180 mg bid or ALXN2050 120 mg bid at Week 26. Percentage change from baseline in proteinuria at Week 50 will be summarized for each treatment sequence group from the MMRM analysis and no formal treatment comparison will be made. In addition, percentage change from re-baseline (ie, Week 26) in proteinuria at Week 50 will also be summarized for each treatment sequence group descriptively.

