In addition to the proteinuria analyses based on 24-hour urine collections, the percentage change from baseline in spot UPCR at each scheduled visit up to Week 50 will also be analyzed using an MMRM model in a similar manner. The plot to present the trajectory of proteinuria over time based on spot UPCR will be visualized by treatment/treatment sequence group.

In addition to the MMRM analysis, observed values, change from baseline, and percent change from baseline in proteinuria will be summarized descriptively by treatment group at baseline and each post-Baseline time point separately by study phase.

The trajectory of proteinuria over time will be visually presented by plotting the mean proteinuria based on 24-hour urine collections at each time point by treatment/treatment sequence group.

4.3.1.2. Reduction in Proteinuria at Weeks 26 and 50 Compared to Baseline (Both Cohorts)

The percentage of participants achieving > 30% and > 50% reduction in proteinuria based on 24-hour urine collection at Weeks 26 and 50 will be summarized by treatment group by calculating the point estimate and 2-sided 95% CI, based on exact confidence limits using the Clopper-Pearson method.

Participants for receipt of additional standard of care therapy (LN cohort only) or treatment discontinuation will be treated as failure to meet the reduction cutoff and considered nonresponders.

A bar chart will also be provided displaying the percentage of participants achieving > 30% and > 50% reduction in proteinuria at Weeks 26 and 50 by treatment group.

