4.4.4. SF-36 (Both Cohorts)

The 36-item Short Form Health Survey (SF-36) version 2 is a set of generic, coherent, and easily administered QoL measures. It has 36 items grouped in 8 dimensions. For both cohorts, the SF-36 total score, Physical Component Summary (PCS), Mental Component Summary (MCS), and domain scores as defined in Table 7 will be summarized by treatment group at baseline and each post-baseline time point using descriptive statistics for continuous variables for the observed value as well as the change from baseline.

The longitudinal changes in SF-36 will be analyzed using MMRM method specified in Section 4.3.1.1 except the log-transformation of SF-36 is not performed. Change from baseline in SF-36 at Weeks 26 and 50 will be summarized for each treatment group from the MMRM analysis and no formal treatment comparison will be made. The point estimate and 2-sided 95% CI for the change from baseline of SF-36 will be presented. Data collected on or after receipt of additional standard of care therapy (LN cohort only) or treatment discontinuation will be assumed missing and handled in the MMRM model as MAR.

Refer to Section 6.3 for a more detailed description of the SF-36 calculation and scoring methods.

Table 7: SF-36 Domain Scores

Scale	Number of Items	Definition of Scale
Physical Functioning (PF)	10	Limitations in physical activity because of health problems
Social Functioning (SF)	2	Limitations in social activities because of physical or emotional problems
Role Limitations Due to Physical Health (RP)	4	Limitations in usual role activities because of physical health problem
Bodily Pain (BP)	2	Prescence of pain and limitations due to pain
General Health (GH)	5	Self-evaluation of personal health
Mental Health (MH)	5	Psychological distress and well-being
Role Limitations Due to Emotional Problems (RE)	3	Limitations in usual role activities because of emotional problems
Vitality (VT)	4	Energy and fatigue

Abbreviation: SF-36 = 36-item Short Form Health Survey

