6.4.2. SAS Code for MMRM Analysis

The secondary endpoint of percentage change from baseline to Week 50 in proteinuria utilizes MMRM analysis. Other secondary endpoints assessing longitudinal changes will also utilize MMRM analysis. Sample code is provided below:

Step 1: Impute data on or after receipt of additional standard of care therapy (LN cohort only) using the value collected at the time of flare or suboptimal response, if applicable

Step 2: Analyze imputed dataset using MMRM analysis-adjust the least square mean estimate based on number of scheduled visit for each of the endpoint/relevant analysis.

where subjid is the participant identifier variable, trt01pn is the randomized treatment group, avisitn is the visit variable, base is the proteinuria value at baseline, strat is the randomization stratification variable, and chg is the change from baseline in log(proteinuria).

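### SAP Table 6 omits rescue for severe extrarenal SLE flare from the LN key secondary intercurrent events, and the MMRM sections do not state one rule for post-rescue data

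*SAP*

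**What the plan says.** Rescue here means what the plan calls additional standard of care therapy in the LN cohort.

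**Which rescue counts.** In both the continuous and binary rows, SAP Table 6 (section 4.3) gives the event as "Receipt of additional standard-of-care therapy for a protocol-defined renal flare or suboptimal response (LN cohort only"). Elsewhere the reason is not restricted:
- The primary estimand (SAP 1.1) lists "Receipt of additional standard of care therapy (LN cohort only) or treatment discontinuation".
- SAP 4.1.4 lists "Receipt of additional standard-of-care therapy (LN cohort only").
- SAP 4.3.1.2 says "Participants for receipt of additional standard of care therapy (LN cohort only) or treatment discontinuation will be treated as failure".
- SAP 4.3.1.10 defines Treatment Failure with three triggers: renal flare, severe extrarenal SLE flare and suboptimal response. Protocol 6.5.4 classes an extrarenal flare as severe once rescue is given for it.

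**What happens to later data.** For Week 50 proteinuria (SAP 4.3.1.1) and for eGFR (SAP 4.3.1.3) the rule is "The data after the intercurrent events will be treated as missing". Neither section names an imputation, and 4.3.1.1 fits all available data up to Week 50. SAP 6.4.2 covers the same Week 50 proteinuria analysis and adds "Other secondary endpoints assessing longitudinal changes will also utilize MMRM analysis". Its Step 1 imputes post-rescue data "using the value collected at the time of flare or suboptimal response, if applicable", and Step 2 fits the MMRM to that imputed dataset.

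**The concern.** SAP 4.3.1.1 and 4.3.1.3 remove only data that follow a listed intercurrent event. If Table 6 supplies the list, rescue for an extrarenal flare is not on it. Week 50 proteinuria and Week 26 and Week 50 eGFR recorded under the added immunosuppression would then enter the MMRMs as observed. CNI rescue is an exception, because study intervention must stop before a CNI starts and treatment discontinuation is a listed event.

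For every rescue type, two programmers could also follow the SAP faithfully and report different numbers, one leaving post-rescue values missing and the other carrying a value forward. The main output affected is the LN Week 50 GMR for 180 mg versus placebo with its 90% CI. The eGFR change estimates are affected too, and so is the spot-UPCR MMRM, which 4.3.1.1 runs in a similar manner. No rescue sensitivity analysis exists for these endpoints: SAP 4.3.2 addresses only the dosing pause.

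**Working it through.** **Texts side by side.** Take an LN participant who receives non-CNI rescue for an extrarenal flare and stays on study treatment.

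| Source | Later continuous values |
|---|---|
| Table 6 read literally, with 4.3.1.1 and 4.3.1.3 | kept as observed |
| Unrestricted list in 4.1.4, with 4.3.1.1 and 4.3.1.3 | missing |
| 6.4.2 Step 1 (no limit on the reason for rescue) | carried forward from the flare |

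In the binary endpoints the same participant is a non-responder, through 4.3.1.2 directly and through the no-Treatment-Failure criterion in 4.3.1.4 and 4.3.1.5. The binary row of Table 6 therefore has no operational effect.

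**Inputs for size.** The plan gives no figure to reproduce here. From Protocol 9.2 and SAP 5: 30 per arm, SD of log change 0.60, and Week 26 ratios to baseline of 0.60 (placebo) and 0.40 (180 mg). Assumed: these ratios also hold at Week 50.

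- SE of log GMR = 0.60 × √(2/30) = 0.155.
- Planned GMR = 0.40/0.60 = 0.667.

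**Table 6 omission.** Assume rescue still lowers UPCR at Week 50 by 0% to 50% relative to the value the MMRM would otherwise imply. Keeping the value moves the arm's log mean by −ln(1.0)/30 to −ln(0.5)/30 in size, that is 0 to 0.0231. The upper end is 0.0231/0.155 = 0.15 SE per participant. With the planned 10% dropout (27 per arm) it is (0.693/27)/(0.60 × √(2/27)) = 0.0257/0.163 = 0.16 SE. The shift is against the drug for a placebo participant and in its favour for a 180 mg participant.

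**Carry-forward versus missing.** A suboptimal response means UPCR at 0.75 of baseline or above (SAP 4.3.1.11). Let rho, from 0 to 1 (assumed), be the correlation between Week 26 and Week 50, and assume the Week 26 value equals the value at suboptimal response. Given Week 26, the MMRM's implicit Week 50 value is mean + rho × (Week 26 value − mean). At the cut-off, carry-forward raises the arm's log mean per participant by:
- placebo: (1 − rho) × (ln 0.75 − ln 0.60)/30 = (1 − rho) × 0.0074
- 180 mg: (1 − rho) × (ln 0.75 − ln 0.40)/30 = (1 − rho) × 0.0210

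Illustrations from GMR 0.667:
- Three such participants per arm: at rho 0 the shift is 3 × (0.0210 − 0.0074), about 0.041, giving 0.694; at rho 0.5, 0.680; at rho 1, 0.667.
- Three on placebo only, rho 0: 0.667 × exp(−0.0223) = 0.652.
- Three on 180 mg only, rho 0: 0.667 × exp(0.0629) = 0.710.

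For a renal flare before Week 26 by the creatinine-plus-proteinuria route (at least 1.75 times baseline, Protocol 8.1.6), with no earlier post-baseline 24-hour value, the per-participant shifts are (ln 1.75 − ln 0.60)/30 = 0.036 on placebo and (ln 1.75 − ln 0.40)/30 = 0.049 on 180 mg.

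A cruder check takes missing values at the unrescued arm mean, with assumed rescue rates of 10% on 180 mg and 20% on placebo. Carry-forward then gives 0.679 if the carried value is 0.75 of baseline and 0.633 if it is 1.5 times baseline. The direction depends on the rescue pattern. The effect on eGFR was not quantified.

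**The case against.** The strongest reply concerns the second part. In this SAP, treating data as missing can be the first step of a rule that then imputes. SAP 4.2.2 does exactly that for the primary analysis: post-event data become missing, and the value at renal flare is then carried forward. SAP 4.1.4 rules out imputation only for missing post-baseline data not due to intercurrent events. On that reading 6.4.2 Step 1 simply supplies the second step.

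This stands to the extent that a reader who infers a flat contradiction goes further than the text allows. It does not remove the ambiguity. SAP 4.2.2 states its second step, 4.3.1.1 and 4.3.1.3 do not, and nothing says when the closing qualifier of 6.4.2 Step 1 applies. For SF-36, analysed with the same MMRM method, SAP 4.4.4 takes the other route, its sentence on rescue ending "LN cohort only) or treatment discontinuation will be assumed missing and handled in the MMRM model as MAR".

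A reader might also infer that carry-forward is the mistake and must go. The documents do not settle that. Carry-forward would match the Week 26 primary analysis. Missing under MAR would make Week 26 and Week 50 proteinuria follow different rescue rules and would assume that rescued participants resemble similar unrescued ones. The sections that spell out MAR (4.4.4, 4.4.5, 4.4.10) concern exploratory patient-reported outcomes.

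On the first part, it is fair to say that the unrestricted wording elsewhere shows the likely intent. Table 6 is nevertheless the stated estimand for these endpoints, and no reason for a narrower event is given.

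**Conclusion.** The Table 6 omission is an error in a stated rule and should be corrected. The post-rescue handling is under-specified: the plan supports two different Week 50 proteinuria estimates and two sets of eGFR estimates.

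The consequence is limited. The secondary analyses are descriptive, eGFR has no formal comparison, and observed-value summaries are planned for both endpoints, so the harm is an estimate that cannot be reproduced from the plan, not lost error control. The omission is worth at most about 0.15 SE of the log GMR per participant, assuming 30 per arm, SD 0.60 and a residual rescue effect of no more than 50%. The carry-forward question can matter more, but its size and sign depend on rescue rates, Week 50 means and a correlation that the documents do not give.

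A reader might infer from the references to renal flare in SAP 4.2.2 that the Week 26 primary analysis has the same gap. The documents do not support that. The primary estimand is unrestricted, the carry-forward in SAP 6.4.1 Step 1 and in Table 4 covers any rescue, and the placebo-based imputation, tipping-point and treatment-policy analyses do too.

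**What to change.** 1. In both rows of Table 6, give the rescue event as receipt of additional standard-of-care therapy for any protocol-defined reason (LN cohort only).
2. State one rule for post-rescue data in 4.3.1.1, 4.3.1.3 and 6.4.2. Either delete 6.4.2 Step 1, so that the data are missing and handled under MAR in the MMRM, or cite the carry-forward in 4.3.1.1 and 4.3.1.3. The choice is the sponsor's.
3. Report the other rule as a sensitivity analysis.

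The cost is a few lines of text and one further model run per endpoint. Under MAR, a few observed post-rescue values leave the MMRMs but remain in the descriptive summaries. Under carry-forward, the text also needs a fallback for an extrarenal flare without a 24-hour urine, because Protocol 8.1.1.1 requires the confirming collection only for renal flare and suboptimal response.

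The sponsor is unblinded at the Week 26 analysis (SAP 1), and the documents do not show whether that has happened. If it has, the change should be recorded as a dated clarification.

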4.3.1. Secondary Endpoints

4.3.1.1. Percentage Change in Proteinuria from Baseline to Week 50 (Both Cohorts)

The percentage change from baseline in proteinuria at Week 50 will be analyzed using a mixed-effect model for repeated-measures (MMRM) using all available data up to Week 50 (either complete or partial). The data after the intercurrent events will be treated as missing. The model will include change from baseline in log-transformed proteinuria as the response variable and fixed, categorical effects of treatment sequence group, randomization stratification factor, visit, and treatment sequence group by visit interaction as well as a fixed, continuous effect of baseline log proteinuria as a covariate. An unstructured covariance matrix will be used to model the correlations among repeated measurements within each participant. If this analysis fails to

converge, a first-order autoregressive covariance matrix will be used. The Kenward-Roger approximation will be used to estimate denominator degrees of freedom.

For the LN cohort, the treatment effect will be evaluated for the ALXN2050 180 mg bid and placebo treatment groups using a contrast for treatment group-by-visit term at Week 50. The point estimate and 2-sided 90% CI for the mean difference of log-transformed proteinuria will be back-transformed (via exponentiation) to obtain the GMR and corresponding 2-sided 90% CI. The values will then be expressed as percentage change in adjusted geometric mean of proteinuria at Week 50 relative to baseline. The treatment effect will be evaluated for the ALXN2050 120 mg & 180 mg bid and placebo treatment group in the same model mentioned above.

For the IgAN cohort, participants initially randomized to the placebo treatment group will switch to receive either ALXN2050 180 mg bid or ALXN2050 120 mg bid at Week 26. Percentage change from baseline in proteinuria at Week 50 will be summarized for each treatment sequence group from the MMRM analysis and no formal treatment comparison will be made. In addition, percentage change from re-baseline (ie, Week 26) in proteinuria at Week 50 will also be summarized for each treatment sequence group descriptively.

In addition to the proteinuria analyses based on 24-hour urine collections, the percentage change from baseline in spot UPCR at each scheduled visit up to Week 50 will also be analyzed using an MMRM model in a similar manner. The plot to present the trajectory of proteinuria over time based on spot UPCR will be visualized by treatment/treatment sequence group.

In addition to the MMRM analysis, observed values, change from baseline, and percent change from baseline in proteinuria will be summarized descriptively by treatment group at baseline and each post-Baseline time point separately by study phase.

The trajectory of proteinuria over time will be visually presented by plotting the mean proteinuria based on 24-hour urine collections at each time point by treatment/treatment sequence group.

4.3.1.2. Reduction in Proteinuria at Weeks 26 and 50 Compared to Baseline (Both Cohorts)

The percentage of participants achieving > 30% and > 50% reduction in proteinuria based on 24-hour urine collection at Weeks 26 and 50 will be summarized by treatment group by calculating the point estimate and 2-sided 95% CI, based on exact confidence limits using the Clopper-Pearson method.

Participants for receipt of additional standard of care therapy (LN cohort only) or treatment discontinuation will be treated as failure to meet the reduction cutoff and considered nonresponders.

A bar chart will also be provided displaying the percentage of participants achieving > 30% and > 50% reduction in proteinuria at Weeks 26 and 50 by treatment group.

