Pregnancy test (WOCBP only)	Х	Х	Х	х	X	X	X	Х	X		Serum tests required at Screening and ED; urine tests at all other visits. (Section 8.2.6)

Table 1: Schedule of Activities During Screening and the Blinded Initial Evaluation Period: Screening to Week 26 Visit (LN Cohort)

Period	Screen- ing		Initial Evaluation Period								Notes
Visit	1	2	3	4	5	6	7	8	9	Evaluation for Renal	Unscheduled visits can be performed as needed. An ED Visit is required if participant discontinues study early.
Week	Up to 6 W		W2	W4	W8	W12	W16	W20	W26/ ED ^b	for Kenal Flare and Extrarenal	
Days and Window	D -42 to -1	D1	D15 ± 3	D29 ± 3	D57 ± 5	D85 ± 5	D113 ± 5	D141 ±5	D183 ± 5	SLE Flare Assessment Visit ²	
FSH test ^d	х										Only for females who are not WOCBP (Section 8.2.4.4).
HIV, HCV, and HBV	X										
Dispense participant safety card	X										Instruct participants to carry safety card at all times and bring it to scheduled visits (Section 8.2.7).
Efficacy Assessments											
24-hour urine collection ^e	х								X	х	One collection is needed as soon as possible during Screening. Two separate collections must be obtained within 2 weeks prior to the Week 26 Visit. (Section 8.1.1.1).
Morning spot urine sample	X	X	X	X	X	X	X	X	X	X	Two consecutive spot urine samples at Week 16 (Section 8.1.2).
eGFR (measured by serum creatinine)	х	х	х	х	х	х	х	Х	х	X	At Week 26, the first creatinine sample for eGFR will be obtained within 2 weeks prior to Week 26 study visit and the second creatinine sample will be obtained on the study visit day (Section 8.1.3).
Predose blood sample for serum clinical complement tests	Х	Х	Х		X		Х		X	X	Section 10.2.

Table 1: Schedule of Activities During Screening and the Blinded Initial Evaluation Period: Screening to Week 26 Visit (LN Cohort)

Period	Screen- ing			Initi	al Evalu		Notes					
Visit	1	2	3	4	5	6	7	8	9	Evaluation for Renal	Unscheduled visits can be performed	
Week	Up to 6 W		W2	W4	W8	W12	W16	W20	W26/ ED ^b	Flare and Extrarenal	Flare and Extrarenal	as needed. An ED Visit is required if participant discontinues study early.
Days and Window	D -42 to -1	D1	D15 ± 3	D29 ± 3	D57 ± 5	D85 ± 5	D113 ±5	D141 ± 5	D183 ± 5	SLE Flare Assessment Visit ^a		
Monitor for Renal Flare and/or Extrarenal SLE Flare ^a			Continuous monitoring							х	Refer to Section 8.1.6 and Section 8.1.7 for definitions. Document use of additional standard of care therapy and/or repeat biopsy, if applicable (Section 6.5.4).	
Safety Assessments												

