4.3.1.3. Change from Baseline in eGFR at Weeks 26 and 50 (Both Cohorts)

Kidney function evaluated by eGFR will be calculated based on the Chronic Kidney Disease Epidemiology Collaboration (CKD-EPI) formula. For participants requiring dialysis for acute kidney injury, a value of 10 mL/min/1.73 m² will be imputed for while participants are on dialysis (ie, from the first day of dialysis through 5 days after the end of dialysis).

For participants in the LN cohort, baseline eGFR will be defined as the lowest measurement available prior to the first dose of study intervention. For participants in the IgAN cohort, baseline eGFR will be defined as the mean of the Screening and Day 1 measurements.

The longitudinal changes in eGFR will be analyzed using the same MMRM method specified in Section 4.3.1.1, but the log-transformation of eGFR is not required. The eGFR will be summarized at baseline and at Weeks 26 and 50 by treatment group using descriptive statistics for the observed value as well as the change from baseline. No formal treatment comparison will be made. The point estimate and 2-sided 95% CI for the change from baseline of eGFR will be presented.

For the IgAN cohort, a similar summary will be made and the change from re-baseline (ie, Week 26) in eGFR at Week 50 will also be presented for each treatment sequence group from the MMRM analysis.

The data after the intercurrent events will be treated as missing.

In addition to the MMRM analysis, observed values, change from baseline, and percent change from baseline in eGFR will be summarized descriptively by treatment group at baseline and each post-Baseline time point separately by study phase.

The trajectory of eGFR over time will be visually presented by plotting the mean eGFR at each time point by treatment group.

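### If the unstructured MMRM fails to converge, the only fallback is AR(1) with one variance for all visits, so Week 50 intervals for spot UPCR and eGFR can be too narrow if spread grows over time

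*SAP*

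**What the plan says.** SAP 4.3.1.1 sets the covariance rule: "An unstructured covariance matrix will be used to model the correlations among repeated measurements within each participant". If that fit fails to converge, "a first-order autoregressive covariance matrix will be used". No other structure is named, and neither is a robust standard error. On inference it adds: "The Kenward-Roger approximation will be used to estimate denominator degrees of freedom". Protocol 9.4.6.2.1 gives the same rule.

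Two larger models take the rule over:

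- **Spot UPCR** (SAP 4.3.1.1): "percentage change from baseline in spot UPCR at each scheduled visit up to Week 50 will also be analyzed using an MMRM model", by what the SAP calls a similar approach.
- **eGFR** (SAP 4.3.1.3): "The longitudinal changes in eGFR will be analyzed using the same MMRM method specified in Section 4.3.1.1", without the log transformation.

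SAP 4.3 and Table 6 list change in eGFR among the key secondary analyses, and SAP 4.3 calls all secondary analyses descriptive. For Week 50 proteinuria in LN, SAP 4.3.1.1 asks for a 2-sided 90% interval for 180 mg against placebo. SAP 4.3.1.3 asks for 2-sided 95% intervals for change in eGFR, with no formal comparison.

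The body of the MMRM sample code in SAP 6.4.2 is absent from the text available for this review, so its covariance and standard-error options could not be checked.

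**The concern.** AR(1) imposes two restrictions that an unstructured matrix does not.

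1. **One variance for all visits.** If change from baseline spreads out over time, the pooled variance is too small for the last visit and too large for the first. A growing spread is plausible: the SAP's own IgAN eGFR slope model (SAP 4.4.13) has random slopes by participant, which would produce it.
2. **Correlation by visit order.** Gaps between visits run from 2 to 8 weeks in both cohorts, yet AR(1) treats adjacent visits as equally spaced.

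Kenward-Roger adjusts degrees of freedom and small-sample bias for the structure that was fitted. It does not repair a wrong structure.

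What is at stake is the stated precision of the Week 50 results for spot UPCR and eGFR. An interval that is too narrow makes a chance difference look firmer than it is.

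**Working it through.** **Inputs from the documents**

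- LN post-baseline visits (Protocol Tables 1 and 3): Weeks 2, 4, 8, 12, 16, 20, 26, 34, 42, 50, which is 10.
- IgAN post-baseline visits (Protocol Tables 2 and 4): Weeks 2, 6, 12, 18, 26, 28, 32, 38, 42, 50, also 10.
- 24-hour collections up to Week 50: Weeks 26 and 50 only.
- Planned sizes: LN 30/10/30; IgAN 24/8/24, with placebo splitting 12/12 after Week 26.
- SD of log change: 0.60 at Week 26 (SAP 5). No other visit has an SD.

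**The plan's own figure.** The SD of 0.60 comes from the LN power statement. With 10% dropout, 30 becomes 27 per arm. The difference is ln(0.60/0.40) = 0.405 and the SE is 0.60 × √(2/27) = 0.163. Power is Φ(0.405/0.163 − 1.645) = 0.799, or 0.790 by noncentral t. The stated 80% reproduces.

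**Covariance parameters for 10 visits**

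| Structure | Count |
|---|---|
| Unstructured | 10 × 11/2 = 55 |
| Heterogeneous Toeplitz | 10 + 9 = 19 |
| Heterogeneous AR(1) | 10 + 1 = 11 |
| AR(1) | 2 |

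**Closed form.** Under AR(1) the fitted SD is close to the root mean square of the visit SDs. With r = pooled SD / true SD at the visit, non-coverage is about 2 × [1 − Φ(z × r)]. It doubles when the true SD exceeds the pooled SD by a factor of 1.645/1.282 = 1.28 (90% interval) or 1.960/1.645 = 1.19 (95% interval).

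Example: SD rising linearly from 0.4 at Week 2 to 0.8 at Week 50, so 0.6 at Week 26. The root mean square over the LN visits is 0.576.

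- Week 50: r = 0.576/0.8 = 0.720, giving 2 × [1 − Φ(1.185)] = 23.6%.
- Week 26: r = 0.576/0.6 = 0.961, giving 11.4%, near the nominal 10%.

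**Simulation, LN spot UPCR, Week 50, 180 mg against placebo.** No treatment effect; AR(1) fitted by REML with treatment by visit, baseline and stratum; 15% dropout assumed; 4,000 runs; normal critical values in place of Kenward-Roger. The SD paths are assumed: linear in time and 0.60 at Week 26.

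| SD, Week 2 to Week 50 | Closed form | AR(1) simulated | Heterogeneous AR(1) |
|---|---|---|---|
| 0.6 to 0.6 | 10.0% | 9.9% | 9.8% |
| 0.5 to 0.7 | 17.0% | 17.3% | not run |
| 0.45 to 0.75 | 20.4% | 21.3% | not run |
| 0.4 to 0.8 | 23.6% | 24.4% | 9.2% |
| 0.3 to 0.9 | 29.2% | 29.9% | 9.3% |
| 0.7 to 0.5 | 4.1% | 4.3% | not run |

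An analysis of Week 50 alone gives 10.2%. Three correlation shapes gave the same picture.

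**eGFR, Week 50, 95% interval for a group mean.** The variance of change is assumed to be 36 + 36 + (weeks/52)² × (slope SD)², with slope SD in mL/min/1.73 m² per year.

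| Slope SD | LN | IgAN (24/8/12/12) |
|---|---|---|
| 0 | 5.4% | not run |
| 8 | 11.3% | 9.0% |
| 12 | 15.4% | 12.4% |

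**Two-visit 24-hour model**, SD 0.6 then 0.8: the pooled SD is √[(0.36 + 0.64)/2] = 0.707 and r = 0.884, so non-coverage is 14.6%. This would apply only if a model with three covariance parameters failed to converge.

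**The case against.** **The fallback may never be used.** Counting 55 parameters against 70 or 56 participants does not show that the fit fails. Unstructured REML fits to 10 visits at the planned sizes converged in 240 of 240 runs, at 10% dropout with 3% intermittent missing and at 20% with 5%. LN at 40% dropout converged in 60 of 60. This stands: at the planned 10% dropout nothing shows that the fallback would be reached. Two limits remain. The optimiser was not the one in SAS. And SAP 4.3.2.1 and 4.3.2.3 rerun the Week 50 proteinuria and eGFR models around the dosing pause, with post-pause data treated as missing or affected participants excluded, so those fits rest on less data. The documents do not say how much less.

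**The growth in SD is assumed.** This also stands. With a flat SD there is no inflation; with a falling SD the intervals are too wide.

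**No formal test is involved.** Correct. The only stated hypothesis is the primary one. Among the 10-visit models, the one comparative interval affected is the LN spot UPCR contrast.

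**A sandwich standard error is no simple cure.** Uncorrected, it is biased low in small groups: non-coverage of a 95% group-mean interval is about 10% at n = 8, 9% at n = 10 and 8% at n = 12. It should not be required.

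**Conclusion.** The point holds as a conditional weakness of low severity. It needs two things together: the unstructured fit fails, and the SD of change grows. For the 90% LN interval to reach double its nominal non-coverage, the SD must rise about 1.6- to 1.7-fold between Weeks 2 and 50; for a 95% interval, about 1.4-fold. Within the assumed range of 0.5–0.7 to 0.4–0.8, non-coverage of the LN spot UPCR interval is about 17% to 25% against 10%. The eGFR intervals miss 9.0% to 15.4% of the time against 5%, under the assumed slope SDs.

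A reader might infer more, and the documents do not support it:

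- **That the trial's error rate doubles.** These analyses are descriptive, so the issue is interval coverage. The primary ANCOVA does not use this covariance model.
- **That Week 26 is also compromised.** Week 26 lies near the middle of the SD path, so its SD is close to the pooled value and coverage stays near nominal.
- **That the Week 50 result from 24-hour urine is at risk.** That model has two scheduled visits and should converge.
- **That the intervals will be too narrow.** They can be; the direction depends on how the SD changes over time, which the documents do not give.

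**What to change.** Replace the fallback sentence in SAP 4.3.1.1 with a fixed order: unstructured; if it does not converge, heterogeneous Toeplitz; then heterogeneous AR(1); homogeneous AR(1) only as a last resort. Keep Kenward-Roger at every step, and do not require an uncorrected sandwich standard error. State that the order applies to every MMRM that refers to 4.3.1.1, including spot UPCR, eGFR and the dosing-pause reruns, and check that the sample code in SAP 6.4.2 agrees. Because protocol 9.4.6.2.1 names AR(1), record the change in SAP 4.8.

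The cost is one sentence and a few more covariance parameters when the fallback is used (19 or 11 against 2), with wider Week 50 intervals if the SD does grow. If the unstructured model converges, nothing changes.
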